# 1.1 Background

# **Clinical Presentation of Progressive Multiple Sclerosis**

Multiple sclerosis (MS) is characterized by inflammatory central nervous system demyelination which can be subclinical or clinical. Clinical attacks typically manifest as optic neuropathy, sensory or motor myelopathy, which worsen over days to weeks and resolve over weeks to months. Most patients recover a significant degree of function following a clinical attack. Although clinical recovery occurs, persistent demyelination or partial remyelination of the lesion is present. The partially denuded axons redistribute sodium-potassium ATPase channels along the axon to compensate for the myelin loss. This results in increased energy expenditure, and loss of signal coherence in the remaining axons. Mitochondrial expansion is necessary within the affected axons to compensate for the increased energy demand. Rapid mitochondrial expansion is associated with defects in mitochondrial replication, which ultimately leads to energy failure in the affected axons, and axonal loss. The stressed neurons subsequently retract synaptic connections and disengage from neural networks, triggering additional metabolic stress and engagement of transcriptional programs that push the neurons, axons, and circuits away from homeostasis. Clinically, this manifests as slow worsening of walking ability in the absence of clinical relapses. The presence of progressive disease does not exclude the presence of inflammatory disease. Medications which have been approved for the treatment of progressive MS, exclusively treat the inflammatory component of the disease. No pharmacologic agent has yet been shown to prevent or reverse neuronal death and axonal loss in MS. This process occurs typically over decades, and appears to be an age dependent phenomenon, with the onset of motor progression becoming apparent in the late fifth decade.

Patients typically have gradual worsening of walking with associated leg spasticity and urinary, bowel and sexual dysfunction. Recent work from our group has shown that progressive motor dysfunction in MS is most common in patients who have spinal cord lesions or lesions in the brainstem involving the motor tracts (Kassa et al., 2021; Keegan et al., 2018; Sechi et al., 2019). This can occur even in the presence of a single cord lesion, and in the absence of brain disease. This provides a good rationale for targeting spinal cord disease as a therapeutic target in patients with progressive MS. Crucially, although progressive MS is characterized by axonal loss, complete loss of axons in any particular tract is unusual, meaning that if conduction block and slowing can be overcome, there is potential to facilitate volitional motor function.

#### Stimulation in MS and SCI

Other research groups have shown benefit of transcutaneous (through the skin) lumbar stimulation in improving spasticity (Keegan et al., 2018), gait dysfunction (Keegan et al., 2018), postural instability (Roberts et al., 2021), and bladder dysfunction (Kreydin et al., 2020) in participants with MS. However continuous use of transcutaneous stimulation is impractical due to the delivery through the skin using an external device, and the results are likely to be short lived in the absence of continued stimulation. By contrast, permanently implanted epidural stimulation leads are widely used in clinical practice for the management of chronic pain. These allow for continuous stimulation which can easily be manipulated to optimize response through means of a remote-control device. Significant progress has been made in the research use of these permanent leads for spinal stimulation in participants with SCI, to enable motor functions previously thought to be permanently lost after SCI. Specifically, Harkema and colleagues reported that, after months of rehabilitation with

permanently implanted spinal stimulators for ES, volitional control of joint-specific muscles and independent standing were achieved by four humans with motor complete paraplegia (Angeli et al., 2014; S. Harkema et al., 2011). Recently, our team reported that the same intervention enabled control of stepping leg movements, which over the course of rehabilitation, translated to independent standing and stepping (M. L. Gill et al., 2018; Grahn et al., 2017).

Our initial case report described that our study goals were achieved within the first few sessions of permanent ES. To summarize, in the first study participant we enrolled, ES Page 7 of 33

enabled: 1) intentional control of motor activity and leg movement; 2) standing; 3) intentional control of step-like movements while side lying with legs suspended in a gravity neutral position, and 4) intentional control of bilateral leg flexion and extension while upright with body weight supported by a harness. More recently, we reported that the same participant achieved independent standing, stepping on a treadmill while using arm support bars to maintain balance, and posture and over ground walking with minimal assistance (M. L. Gill et al., 2018). To date, the second participant demonstrated similar ES-enabled motor achievements. In addition to reports of ES enabling lower extremity motor functions, improvements in upper extremity(Lu et al., 2016), cardiovascular (Aslan et al., 2018; S. J. Harkema, Legg Ditterline, et al., 2018; S. J. Harkema, Wang, et al., 2018; Herrity et al., 2018; West et al., 2018), and urologic functions (Herrity et al., 2018) have been reported in participants with SCI.

Prior to proposing a trial to assess the use of permanently implanted epidural spinal stimulation in participants with progressive MS, it is pertinent to assess whether these individuals are responsive to stimulation using a temporary percutaneous lead used commonly in clinical practice for low back pain and in research for participants with spinal cord injury.

[figure not shown]
# **1.2 Investigational Device**

Abbott percutaneous trial lead for epidural neurostimulation (Model 3086)

Ripple Nomad Neurostimulator

Abbott clinician programmer (Model 3874)

The temporary percutaneous implantation of epidural stimulation (ES) electrode leads along the dorsal epidural surface of the lumbosacral enlargement (Figure 1) will be performed to activate spinal networks in ten humans diagnosed with Progressive MS. The externalized ends of the ES electrode leads will be connected to the Nomad neurostimulation system. By delivering ES over the spinal cord during task-specific training for one month, we

**Figure 1.** Epidural stimulation (ES) will be delivered via percutaneous electrodes implanted over the dura mater of the lumbosacral enlargement.

aim to quantify motor and non-motor improvements.

# 1.3 Preclinical Data

Several decades of human investigation have focused on using ES to activate what was thought to be isolated spinal circuitry below the level of functionally complete SCI in order to study central pattern generator activity (Dimitrijevic et al. 1998; Jilge et al. 2004; Minassian et al. 2004; Roy et al. 2012) In 2011, Harkema and colleagues published a landmark report that after months of training, ES facilitated intentional control of joint-

Page 8 of 33 [name]. specific muscles and independent standing by a human with motor complete paraplegia (Harkema et al. 2011). The same research group successfully replicated their results in three additional subjects (Rejc et al. 2015; Rejc et al. 2017; Angeli et al. 2014). Based on these results, we initiated a clinical trial (NCT02592668) and in 2017, we reported successful replication of Harkema et al., along with additional outcomes (Grahn et al. 2017). Based on observations made during NCT02592668, we have designed this protocol to gain additional scientific knowledge with respect to how ES may enable functions in humans with multiple sclerosis.

# 1.4 Study Rationale and Risk Analysis (Risks to Benefits Ratio)

# 1.4.1 Study Rationale

There is no cure for MS, which results in gradual loss of many functions and a significant reduction in quality of life. In parallel, there is no cure for traumatic injury of the spinal cord which results in lifelong impairment of autonomic, sensory, and motor functions in regions of the body that are distal to the damaged areas of the spinal cord. In response to the complete lack of available therapies to restore volitionally-controlled lower extremity motor function, we recently conducted a pilot-phase clinical trial of epidural spinal electrical stimulation (ES) in combination with task-specific training for individuals with complete SCI. Likewise, other research teams have shown remarkable improvements in spinal stimulation-enabled motor functions that are retained after study participation in individuals with incomplete paralysis (Wagner et al., 2018). Herein, we propose leveraging the knowledge and expertise gained during our previous, and active, clinical trials of ES in participants with paralysis to determine the translational potential of ES for improvement of motor function and spasticity in patients with myelopathy due to progressive MS. Completion of the proposed experiments in this protocol will provide data that can be used to improve the scientific understanding of how ES may enable functional improvement after MS onset. This knowledge will be used to help determine if ES is a viable and useful tool in determining which subjects may be best suited for permanently implanted ES in the future.

# 1.4.2 Anticipated Risks

# **Risks associated with task-specific training:**

In combination with ES, the rehabilitation techniques used during this study will focus on maximizing independence, load bearing, body position, and kinematics during motor tasks while providing the minimum amount of trainer assistance and body weight support necessary to safely perform tasks. Risks associated with daily training include skin irritation and minor bruising from pressure applied during trainer assistance and body weight support, musculoskeletal discomfort, fatigue, and bladder or bowel incontinence due to exertion and

abdominal pressure from support harness. There is a slight risk of fracture in the lower extremities. Orthostatic hypotension is a risk associated with abrupt position changes against gravity, specifically transitioning from sit to stand quickly.

# Risks associated with weight-bearing tasks:

Risks include muscle soreness, fatigue, skin irritation, fracture, changes in blood pressure, and potential for a fall.

# Risks associated with temporary percutaneous implantation of ES electrode leads:

ES electrodes will be implanted via commonly used percutaneous implantation techniques for FDA-approved treatment of medically refractory pain conditions. Therefore, the risks associated with percutaneous implantation of the ES system for this study match the risks associated with ES system implantation for treatment of FDA-approved conditions.

- Undesirable changes in stimulation may occur over time. These changes in stimulation are possibly related to cellular changes in tissue around the electrodes, changes in the electrode position, loose electrical connections and/or lead failure.
- Placement of a lead in the epidural space is a surgical procedure that may expose the patient to risks of epidural hemorrhage, hematoma, infection, spinal cord compression, and/or paralysis.
- Radicular chest wall stimulation.
- Cerebrospinal fluid (CSF) leakage.
- Persistent pain at the electrode site or receiver site.
- Seroma at the incision site.
- Implant migration.
- Allergic or rejection response to implant materials.
- Lead migration and/or local skin erosion.
- Paralysis, weakness, clumsiness, numbness, or pain below the level of implantation.

#### **Risks associated with ES following implantation:**

Hardware malfunction, discomfort or abdominal tightness during ES, increased or decreased spasticity, bowel or bladder incontinence, shortness of breath, muscle soreness, or fatigue may occur during ES. Autonomic dysreflexia is a possible risk factor for subjects as well.

#### **Risks associated with MRI**

Dislodgement of some metal implants and claustrophobia may occur during MRI. Subjects will be rigorously screened in the same fashion as clinical patient by MRI technicians prior to each scan. Earplugs will also be provided to keep MRI noise within a safe audible range. Due to the potential for tissue heating, image artifacts, induced voltages in the neurostimulator or leads, and lead dislodgement, MRIs will not be obtained after epidural stimulator implantation.

#### **Risks associated with electromyography**

Risks involved with EMG include skin irritation or allergic reaction from the adhesive used to apply sensors.

# Steps taken to minimize the occurrence and severity of associated risks:

Trained study staff and medical technicians will directly oversee all tasks. Body weight support, a safety gait belt, and other safety measures as necessary will be utilized to lessen the risks involved with rehabilitation and weight-bearing tasks. To mitigate risks in general, the protocol will be conducted as stated, medical professionals will be consulted, and care will be provided to address any study-related concerns that arise. All members of the research team will be trained to identify the occurrence of risks related to this study. If risk occurrence is observed, study-related activities will be halted until appropriate medical care

is given and it is deemed safe for the subject to continue study-related activities. Because the interventions have been used for individuals with subjects with spinal cord injury and subjects will have been carefully screened, we do not anticipate any serious adverse events in this study. However, if they do occur, serious adverse events will be reported to the PI, medical monitor, IRB and FDA within the appropriate reporting timeframes. Adverse events will be reported to the PI, the site medical monitors IRB, and FDA within the appropriate reporting timeframes.

# 1.4.3 Potential Benefits

The benefits which may result from this research study may include recovery of sensorimotor function, recovery of bladder, bowel, or sexual function, improved thermoregulation, improved body mass composition, and improved sense of wellbeing. The certainty and degree to which these benefits may or may not occur is unknown.

# 1.5 Anticipated Duration of the Clinical Investigation

The anticipated duration of study participation for each human subject is approximately 2 months. Subjects will receive ES and task-specific training sessions for 1 month. Electrodes will be removed following 1 month of sessions.

# 2 Study Objectives

We propose to compare motor and non-motor outcomes over the course of 1 month of ES in combination with task-specific training in participants with Progressive MS.

# 2.1 Primary Objective

The primary objective is to evaluate the effectiveness of percutaneous ES and task-specific training over 1 month in participants with Progressive MS to impact motor function and spasticity.

# 2.2 Secondary Objective

The secondary objective is to investigate the potential of ES and task-specific training to impact non-motor spinal related dysfunction in the same participants with Progressive MS.

# 3 Study Design

# 3.1 General Design

This is a pilot study that will include a total of 10 subjects with Progressive MS (EDSS 6.5). All subjects will complete 1 month of ES and task-specific training. Expected duration of subject participation is less than 2 months. Baseline assessments will be obtained prior to implantation and post-stimulation assessments will be obtained prior to explantation, with stimulation on and off.

SCREENING	BASELINE	STIMULATION	POST- STIMULATION	
	Baseline Assessments	Minimum 12 Sessions	End Assessments	
Assessment of Inclusion/Exclusion criteria by study team	Clinical, Electromyography, Movement Assessments& Surveys	Stimulation + Task- Specific Training	Clinical, Electromyography, Movement Assessments & Surveys	STUDY END
	No Stim	Percutaneous Stimulation	Stim on/Stim off	
l-month pre- enrollment	Week 0-1	Weeks 1-4	Week 4-5	

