- The proposed research is a pilot study which will explore epidural spinal stimulation (ES) in combination with task-specific training to improve lower limb function in 10 participants with Progressive MS.
- We will temporarily implant percutaneous ES leads through the skin overlying the lumbosacral enlargement and remove the leads following the 4-week study.
- Participants will serve as their own control via a comparison of pre- and poststimulation outcomes and outcome metrics captured during ES and when ES is off.
- Safety will be continuously evaluated during the 4-week stimulation and task specific training period, and during a post lead removal neurologist visit.
- The percutaneous leads are currently used clinically and are approved for patients with low back pain; use in participants with MS will be possible under an FDA IDE.

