# 5 Study Device

# 5.1 Description

# Epidural spinal cord stimulator (Model 3086, Abbott Neuromodulation; Nomad, Ripple Neuro)

The ES electrode lead is an implantable neurostimulation device that is FDA-approved for treatment of neuropathic pain disorders. Up to two ES electrode leads will be implanted temporarily along the dorsal epidural surface of the lumbosacral enlargement (i.e., L2-S1 spinal segments). The externalized ends of the ES electrode leads will be connected to the Nomad neurostimulation system to deliver electrical pulse waveforms to the epidural surface.

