# 5.3 Preparation and Administration/Implantation of Investigational Device

[figure not shown]
Description of ES system implantation/administration

We recently published a detailed explanation of the procedure to implant a permanent

electrode array connected to an implanted pulse generator, along with a detailed description of the electrophysiological approach used to guide electrode positioning over the lumbosacral enlargement in humans with SCI (Calvert, 2018). The same approach will be used during this study to guide electrode placement via electrophysiological monitoring of spinal motor evoked potentials.

The procedures for percutaneously implanting Abbott ES electrodes are performed daily at Mayo Clinic to treat patients suffering from neuropathic pain. Prior to implantation, subjects will undergo a pre-operative evaluation to minimize the risk of unexpected complications. Pre-operative assessments may be performed to check for any signs of infection.

To implant the temporary spinal electrodes, under fluoroscopy an electrode insertion needle will be placed into the epidural space using a paramedian approach and loss of resistance technique to advance through the ligamentum flavum, followed by fluoroscopic visualization of the needle's position. Once positioning is confirmed, the needle stylet will be removed, and the needle will be advancedinto the epidural space.

Then, the leads are advanced in an anterograde fashion to the level of the lumbosacral enlargement utilizing fluoroscopic guidance. Following electrophysiologic confirmation of electrode positioning, the needle and stylet will be removed, the implantation site will be dressed, and the leads will be secured to the skin via an adhesive bandage. The implantation site will be monitored for signs of infection, tissue erosion, or dislodged lead wires. One day post implantation, the first follow up will take place to evaluate for adverse events. Trained

Page 16 of 33 [name]. team members will monitor the percutaneous site on an ongoing basis during training session to ensure the site remains intact and sterile. Study team members have received training from a registered nurse within the pain specialty program at Mayo Clinic.

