#### Procedure to explant ES electrode leads

After completing task-specific training with ES, the adhesive bandage covering the implantation site will be removed, the incision site will be opened, and the leads will be carefully retracted. Finally, the incision site will be cleaned and dressed.

If complications associated with temporary lead implantation (e.g., infection, severe lead migration, device malfunction, etc.) are observed, the PI will make an informed decision whether to perform explantation prior to completion of task-specific training. Participants will be followed up within 5 days of explantation for adverse events. They will be provided information for monitoring the site remotely as well.

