# 7.2 Statistical Methods

*Statistical Methods:* Continuous data will be summarized as median (inner quartile range). Categorical data will be presented as frequency (percentage). Graphical presentations of subject-level data will be used for all endpoints. Individual data points will be plotted over time, from pre to post stimulation and training.

*Modeling:* Statistical models will be used both to estimate the ES effect on endpoints, as well as to provide estimates of variability to enable sample size estimation for future studies. Models for post-ES treatment will be fit using linear regression using the baseline measure as a covariate. Both the ES treatment effect and the residual variance estimate will be reported. Standard deviations of the differences in pre- and post-ES measurements will also be reported. Furthermore, correlations between pre- and post-ES assessments, as well as post task specific training stim-off and stim-on assessments will be calculated to aid future study design. Transformations of endpoints to achieve symmetry in the distribution (normality will be difficult to assess with this sample size) will be used as necessary.

*Handling of Missing Data:* Due to the small sample size, sophisticated missing data techniques like imputation are likely to be unreliable. For all analyses, only subjects with complete data for the necessary analysis will be included. We will attempt to limit missing data by only enrolling participants who have the physical capacity to complete the training sessions. Only prospective enrollees who have been fully optimized from a rehabilitation point of view will be offered enrollment in the study. To minimize the financial burden on study participants and their families, they will be offered money to offset the cost of travel and accommodation during the study. If a study participant ends the study early, a similar replacement participant will be sought. Missing data in survey instruments will be minimized by allocating time during the study for survey completion, and inspection for completion by study coordinators before moving to the next component of the study.

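### The pre-to-post change that section 7.2 calls the ES effect cannot separate stimulation from training, time, carry-over and the presence of externalised leads

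*Combined protocol and SAP*

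**What the plan says.** Section 3.1 fixes the timing of both assessments: "Baseline assessments will be obtained prior to implantation and post-stimulation assessments will be obtained prior to explantation, with stimulation on and off". The outcome tables in sections 3 and 6.4 agree. Gait analysis, voluntary movement, spasticity, TUG and MSQLI are measured at wk 0 without stimulation and at wk 4/5 under a heading that covers ON and OFF. Only voluntary movement has further readings, at wk 1 and wk 4, in the columns for the stimulation and training period. No outcome measure is scheduled after lead removal.

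On the leads, section 5.1 says "The externalized ends of the ES electrode leads will be connected to the Nomad neurostimulation system" and section 5.3 says "the leads will be secured to the skin via an adhesive bandage". The risk list in section 1.4.2 includes "Persistent pain at the electrode site or receiver site", and also weakness, clumsiness or numbness below the implant level.

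On control and analysis, section 1 says "Participants will serve as their own control via a comparison of pre- and poststimulation outcomes", and adds a comparison of ES on with ES off. All subjects receive ES with training (5.2) and nobody is blinded (5.7). Section 7.2 says "Models for post-ES treatment will be fit using linear regression using the baseline measure as a covariate", and that the ES treatment effect and residual variance will be reported. It also plans SDs of the pre-post differences. For stim-on and stim-off it plans a correlation and no estimate of the difference.

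Two contacts follow removal. Section 1 has safety evaluated "during a post lead removal neurologist visit". Section 5.3 says: "Participants will be followed up within 5 days of explantation for adverse events".

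**The concern.** Baseline and post differ in more than training and stimulation: the leads are absent at one and present at the other. Externalised leads taped to the back could alter how someone at EDSS 6.5 walks, stands, rises from a chair or relaxes a limb. Discomfort or guarding could hide a gain, and altered tone or guarding could look like a change in spasticity.

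Two uses of the results are at stake. A reader will take the quantity in 7.2 as what stimulation did, although it holds several components. The pre-post SDs and correlations are also meant for sizing later studies, and section 1.4.1 looks ahead to permanently implanted systems, where any effect of temporary externalised leads need not carry over.

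**Working it through.** The plan states no power, significance level or effect size (7.1), so there is no planned figure to reproduce. The check is which effects the scheduled readings can identify.

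**Step 1. The three states common to all outcomes.** Let m be the baseline level, L the effect of having leads in place, T everything that accrues over the month (training, time, practice, ES carry-over), and S the immediate effect of stimulation being on. Assume these add.

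| Reading | Leads | Stimulation | Expected value |
|---|---|---|---|
| Baseline, wk 0 | out | off | m |
| Post OFF, wk 4/5 | in | off | m + L + T |
| Post ON, wk 4/5 | in | on | m + L + T + S |

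**Step 2. The contrasts.**
- Post OFF minus baseline = L + T
- Post ON minus baseline = L + T + S
- Post ON minus post OFF = S

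In the order (m, L, T, S), the design rows are (1,0,0,0), (1,1,1,0) and (1,1,1,1): rank 3 for four unknowns. Adding the row for L alone, (0,1,0,0), raises the rank to 4, so L is not estimable. The same holds for T alone. The rows for L + T and for S leave the rank at 3, so both are estimable. More subjects would not change this.

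**Step 3. What the 7.2 model does.** In one group, a least-squares line of post on baseline passes through the two means. At the mean baseline, the fitted post value minus baseline is the mean change: L + T with the OFF reading, L + T + S with the ON reading. Covariate adjustment does not remove L.

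**Step 4. Voluntary movement.** The wk 1 and wk 4 readings fall in the stimulation period, with leads in at both. If the lead effect is the same in both weeks and the stimulation state is the same, wk 4 minus wk 1 cancels L and S and leaves the part of T that accrues between them. The tables do not give the stimulation state, or the timing of the wk 1 reading relative to the first training session.

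**Step 5. A reading after removal.** In the additive model, a lead-free post row (1,0,1,0) raises the rank to 4 and makes L formally estimable. In practice, let F be carry-over lost by then and R the effect of removal-site soreness and retesting. The reading is m + T − F + R, and post OFF minus this reading is L + F − R, which is not L alone.

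**Step 6. Scale, by assumption only.** With n = 10, the 95% half-width for a mean change is t(0.975, 9)/√10 = 2.262/3.162 = 0.715 SD of the change. Rejection rates below are for a two-sided 5% paired t-test when the lead shift is the only effect. The 5% level and the shifts are assumptions. The Study Summary names repeated measures ANOVA for pre-to-post change, which with two readings is equivalent to the paired t-test, but gives no level.

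| Assumed lead shift (SD) | Share of half-width | Rejection rate |
|---|---|---|
| 0 | 0% | 5.0% |
| 0.1 | 0.1/0.715 = 14% | 5.9% |
| 0.2 | 0.2/0.715 = 28% | 8.8% |
| 0.3 | 0.3/0.715 = 42% | 13.6% |
| 0.5 | 0.5/0.715 = 70% | 29.3% |

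A shift in the other direction would mask a benefit instead.

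**The case against.** The strongest reply is that the primary objective (2.1) concerns percutaneous ES with training as a package. Leads are part of percutaneous ES, and no objective claims a lasting lead-free effect. Section 1.1 asks whether these people respond to stimulation through a temporary lead, which ON versus OFF addresses. This stands in part: the combined change is a legitimate quantity if it is named as combined. It does not justify calling it the ES effect, and 7.2 gives no estimate for the contrast that answers the responsiveness question.

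The second reply is that baseline-to-OFF in an unblinded single-arm pilot already mixes training, practice, time and carry-over, so leads are one more component of unknown size. That is correct, and it is why the remedy is mainly analysis and labelling.

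A reader might go further in three ways that the documents do not support:
- **That the reported effect is biased by the leads.** No lead effect is given. A list of possible complications is not evidence of a mean shift, and the shifts in the scale table have no source in the documents.
- **That no collected reading holds lead status constant over time.** For voluntary movement, the wk 1 and wk 4 readings do.
- **That a test soon after removal restores the baseline state and isolates the lead effect.** Section 5.3 has the site opened at removal, so soreness, fading and retesting enter. With a half-width of 0.72 SD, 10 subjects could not resolve a shift of 0.5 SD or less in any case.

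**Conclusion.** The point holds as one of attribution. From section 3.1 and the outcome tables, the pre-to-post change cannot separate lead presence from training, time and practice, and ES carry-over; if the ON reading is used, it also contains immediate stimulation. The size and direction of a lead effect are unknown, and it may be negligible.

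ON minus OFF at wk 4/5 is free of lead presence because leads are in for both readings. It remains unblinded, and the order of the two conditions is not stated.

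The non-separability needs only the stated timing. The cancellation of L in ON minus OFF, and in wk 4 minus wk 1, assumes additive effects and a lead effect that is the same at the readings compared. The point limits what the trial can attribute to ES; it does not undermine the safety data or the descriptive summaries.

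**What to change.** Change section 7.2 as follows; all three items use data already scheduled.

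1. Estimate the within-subject ON minus OFF difference at wk 4/5, with a confidence interval, as the immediate ES effect. State the order in which the conditions were tested. If MSQLI is completed only once at the post time point, say that it has no such contrast.
2. Report baseline-to-OFF separately, labelled as the combined effect of training, time, ES carry-over and indwelling leads. Say which reading feeds the regression and the pre-post SDs, and do not call the result the ES effect.
3. For voluntary movement, also report the wk 1 to wk 4 change, which holds lead status constant, and give the stimulation state at each reading.

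The cost is SAP wording and a few lines of analysis.

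Optional addition: repeat TUG and the spasticity test at the post-removal neurologist visit in section 1, as a descriptive lead-free reading for those two outcomes only. A working estimate is 15 to 30 minutes per subject. The visit has no stated date, is listed for safety, and is not said to be the 5-day contact in 5.3, so the protocol would need to give its timing and confirm that it is in person with testing staff. The report should note that removal-site soreness, fading of ES and retest effects may influence the reading, and that it does not isolate a lead effect.
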